Glucose and FFA are the two major substrates used for the synthesis of triglycerides in WAT. We have developed a fluorescent-based approach for simultaneous measurement of glucose and FFA uptake using green fluorescent 2-NBD-glucose and red fluorescent BODIPY-C12(97) (**Figure 7**). This approach will allow determination of insulin sensitivity and lipid and glucose accumulation of primary WAT explants. In addition, small soleus muscle biopsies will be analyzed for insulin sensitivity using 2-NBD-glucose (**Figure 8**).

Anticipated results:

Mirroring increases in ectopic fat we expect to see in Aim 1, we anticipate that intralipid infusion, but not infusion of the control solution, will increase plasma FFA's associated with increased muscle and adipose triglycerides and DAG's in all FAO patients and controls (**Figure 5**). Plasma and tissue long-chain acylcarnitines will be greatly elevated in CPT2, VLCAD or LCHAD/TFP-deficient subjects; medium-chain acylcarnitines will be greatly elevated among subjects with MCAD deficiency; and both long-chain and medium-chain acylcarnitines will be only modestly elevated in normal controls. Based on our preliminary data, we expect that short-chain acylcarnitines may be elevated in subjects with CPT2, VLCAD, LCHAD/TFP, and MCAD deficiency compared to controls.

We predict that these cellular changes will be associated with a decrease in phospho-(p)IR and pAKT and an increase in pPKC- Θ in subjects with MCAD deficiency and control subjects, but not in CPT2, VLCAD, and LCHAD/TFP-deficient subjects, paralleling the expected outcomes of system insulin sensitivity measurements obtained by the HEC's in Aim 1. These expected decreases in insulin signaling pathway component expression and activation will also be reflected by decreased glucose uptake into muscle and adipose tissue and decreased FFA uptake into adipose in controls and subjects with MCAD deficiency. Decreased glucose uptake will be correlated with medium-chain acylcarnitines, as has been reported in human studies(52) and in cultured myocytes.(52) We anticipate no change in glucose and FFA uptake in muscle or adipose tissue from the glycerol/saline to the intralipid co-infusion samples in CPT2, VLCAD and LCHAD/TFP-deficient subjects.

[figure not shown]
Figure 8: Fluorescence analysis of glucose uptake in monkey skeletal muscle.

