Skeletal muscle (vastus lateralis) explants obtained at necropsy from a female rhesus macaque were treated with 10 nM insulin at 37°C for 30 min., followed by 0.05 mM 2-NBD-glucose for an additional 30 min., and analyzed by confocal microscopy. A) Upper panels are images of longitudinal muscle fibers and lower panels are cross-sectional images of muscle fiber bundles. Bars are means \pm SEM of 36 individual muscle fibers. Scale bar=50 μ m; f.u.=fluorescent units. 2-NBD-glucose incorporation into individual fibers was quantified using image J. Mean fluorescence per fiber was determined using a randomly positioned circular region of interest of cross-sectional images.

Metabolites will be measured by metabolomics, including the acylcarnitines, amino acids, organic acids and ketone bodies (**Figure 5**). Based on previous observations, we anticipate controls will have a decrease in plasma BCAAs,(72) but we anticipate normal amino acid profiles among subjects with a FAO disorder.(30) Tissue long-chain acylcarnitines will be much higher and ketones such as acetoacetate will be lower in CPT2, VLCAD and LCHAD/TFP-deficient subjects compared to controls due to the decreased long-chain FAO. Subjects with MCAD deficiency will have higher medium-chain acylcarnitines compared to subjects with long-chain FAO disorders and ketone concentrations similar to controls.

Figure 7: Concurrent measurement of FFA and glucose uptake in WAT explants.

Subcutaneous biopsy-derived WAT explants from a female rhesus macaque were pretreated for 1 hour with basal or 10 nM insulin-containing media. Explants were co-labeled with 2-NBD-glucose and BODIPY-C12, imaged using confocal microscopy, and processed as described. Green patches enriched in 2-NBD-glucose represent adipocyte cytoplasm. BODIPY-C12 accumulates in large and small lipid droplets (red). Scale =10 μ m.

II.

Study Population

Subjects with a fatty acid oxidation disorder:

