saline/2.5% glycerol or 20% intralipid infusion of 1.5 ml/min will be started and continued until the 5-hour clamp has been completed and the muscle and fat biopsy have been performed. Blood glucose will be monitored every 5-10 min during the insulin infusion using a Hemocue Glucose 201(HemoCue America, Brea, CA), or an i-STAT analyzer (Abbott Point of Care Inc, Abbott Park, IL) and euglycemia will be maintained throughout the clamp by infusing 20% dextrose at a variable rate. To maintain a constant enrichment of [6,6-²H₂] glucose in blood during the clamp, [6,6-²H₂] glucose infusion will be continued throughout the clamp and at 2% enrichment in the 20% dextrose solution. Additional blood samples will be collected every 60 minutes for insulin, ketones, and FFA, and at the beginning and end of the clamp for ²H₂-glucose and metabolomics. Using the blood samples collected during the 30-minute period just preceding and at the end of the glucose clamp, glucose disposal rates (Rd) and basal endogenous glucose production (R_a) will be calculated according to the steady-state equations of Steele.(92) At the end of the 5 hour infusion and completion of the muscle and fat biopsies, the insulin and intralipid or glycerol/saline infusions will be stopped. After 10 minutes, the subject will be fed a low-fat meal. Blood glucose will continue to be monitored for an additional hour after the insulin infusion is stopped with adjustment to the glucose infusion as indicated to ensure subjects reestablish endogenous glucose regulation.

Rationale for HEC approach: Patients will undergo insulin sensitivity measurement using HECs along with determination of ectopic fat accumulation by ¹H magnetic resonance spectroscopy (MRS). If the defective mitochondrial function and "lipotoxicity" hypothesis is true, then insulin resistance should be common among patients with long-chain FAO disorders in whom FAO capacity is greatly reduced. However, insulin resistance and diabetes have not been previously reported in case reports of patients with CPT2, VLCAD, or LCHAD/TFP deficiency(35) and, in our preliminary data(30) (see also above), these patients have comparable levels of IMCL, IHL, and glucose tolerance to controls while consuming a low-fat diet.

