Metabolomics: Plasma, muscle, and subcutaneous adipose tissue aliquots will be extracted, derivatized, centrifuged, decanted and dried as previously described.⁴² A set of 13 C8-C30 fatty acid methyl ester internal standards will be added, samples derivatized, and analytes separated using an Agilent 6890 gas chromatograph (Santa Clara, CA). Chromatography will be performed followed by mass spectrometry by a Leco Pegasus IV time-of-flight mass spectrometer (St. Joseph, MI) with 280°C transfer line temperature, electron ionization at 270eV and an ion source temperature of 250°C. Mass spectra will be acquired from m/z 85–500 at 17 spectra s21 and 1850 V detector voltage. Result files will be exported to our servers and further processed by the metabolomics BinBase database. All database entries in BinBase will be matched against the Fiehn mass spectral library of 1,200 authentic metabolite spectra. Identified metabolites will be reported if present within at least 50% of the samples per study design group. Peak heights of quantifier ions defined for each metabolite in BinBase will be normalized to the sum intensities of all known metabolites and used for statistical investigation. Compiled data sets will be analyzed using an appropriate array of multivariate data analyses techniques including principal components analysis, hierarchical cluster analyses, and projection to latent structures discriminant analyses using the an R-based Microsoft Excel Add-in developed in the laboratory of [name] and SIMPCA-P v.12.0.

Laboratory analysis of Tissue Biopsies: Subcutaneous WAT and muscle biopsies will be processed for explant assays of glucose and FFA uptake as well as for the preparation of lysates for Western immunoblot

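### Metabolite peaks are divided by a total that the plan itself expects to change with infusion and diagnosis, so the Aim 2 metabolomics comparisons may be biased in either direction

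*Combined protocol and SAP*

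**What the plan says.** Section IV, Laboratory Methods, Metabolomics, describes one method for plasma, muscle and adipose tissue, and one normaliser. Quantifier-ion peak heights "will be normalized to the sum intensities of all known metabolites and used for statistical investigation". The normalised data then go to principal components, clustering and discriminant analyses. Internal standards are used ("A set of 13 C8-C30 fatty acid methyl ester internal standards will be added"), but the section does not make them the normaliser. It describes no log-ratio, restricted denominator, absolute quantification or check that the total is stable.

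On what is measured, Specific Aim 2 names lipids, oxidation intermediates and amino acids. The Aim 2 anticipated results add: "Metabolites will be measured by metabolomics, including the acylcarnitines, amino acids, organic acids and ketone bodies".

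On what is expected to change, the same part of the protocol says that the lipid infusion "will increase plasma FFA's associated with increased muscle and adipose triglycerides and DAG's in all FAO patients and controls". For the long-chain disorders it says: "Plasma and tissue long-chain acylcarnitines will be greatly elevated in CPT2, VLCAD or LCHAD/TFP-deficient subjects". Medium-chain species are expected to be much higher in MCAD deficiency, and both classes only slightly raised in controls. For amino acids, "we anticipate controls will have a decrease in plasma BCAAs", with normal profiles expected in patients.

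Section III gives the two infusions: "saline/2.5% glycerol or 20% intralipid infusion of 1.5 ml/min will be started". Section V takes the within-subject difference between infusions as the dependent variable and compares it between patients and matched controls.

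**The concern.** Dividing by the sum of all known metabolites is neutral only if that sum is unaffected by the conditions being compared. Here it contains responses under study. If the sum moves, every other metabolite moves the opposite way, whether or not its concentration changed.

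Two kinds of Aim 2 statement are exposed. The first is amino acid profiles, for which no separate assay is listed. The second is the contrast between long-chain and medium-chain acylcarnitines, which is central to the study's model. If long-chain species enlarge the total in CPT2, VLCAD and LCHAD/TFP patients, their normalised medium-chain values are pushed down, in the direction that the model favours.

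**Working it through.** The plan states no figure for this step, so there is none to reproduce. The check is arithmetic on a closed sum.

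**Inputs from the documents.** The normalisation rule (Metabolomics); the expected changes (Aim 2 anticipated results); both infusions at 1.5 ml/min for 5 h (Section III); 8 patients per diagnosis, each with a matched control (Section II); level 0.05 per comparison (Section V). With the percentages read as g per 100 ml (an assumption), the infusions deliver about 0.20 × 1.5 × 300 = 90 g of lipid or 0.025 × 1.5 × 300 = 11.25 g of glycerol. These are masses infused. They do not give shares of measured signal.

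**Assumed inputs.** f is the share of total signal that rises r-fold on the lipid day. g is the share that rises q-fold on the glycerol day. The documents give none of these.

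**Step 1: no glycerol offset.** The apparent lipid/glycerol ratio of an unchanged metabolite is 1 / [1 + f(r − 1)].

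| f | r = 2 | r = 3 |
|---|---|---|
| 0.02 | 0.980 | 0.962 |
| 0.05 | 0.952 | 0.909 |
| 0.10 | 0.909 | 0.833 |
| 0.20 | 0.833 | 0.714 |
| 0.30 | 0.769 | 0.625 |

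The apparent fall runs from 2% (1/1.02) to about 38% (1/1.60).

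**Step 2: glycerol also raises the control-day sum.** The ratio becomes [1 + g(q − 1)] / [1 + f(r − 1)].

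- f = 0.20, r = 3, g = 0.05, q = 3: 1.10/1.40 = 0.79, still a fall.
- f = 0.10, r = 2, g = 0.05, q = 3: 1.10/1.10 = 1.00, no bias.
- f = 0.05, r = 2, g = 0.05, q = 5: 1.20/1.05 = 1.14, an apparent rise.

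**Step 3: patient versus control on the log scale.** The spurious ratio of ratios is [1 + f(r_control − 1)] / [1 + f(r_patient − 1)]. It equals 1.00 if both groups' sums rise equally. Otherwise:

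- f = 0.05, 3-fold in patients against 2-fold in controls: 1.05/1.10 = 0.95.
- f = 0.10, 3 against 2: 1.10/1.20 = 0.92.
- f = 0.20, 3 against 2: 1.20/1.40 = 0.86.
- f = 0.20, 5 against 3: 1.40/1.80 = 0.78.

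**Step 4: patient versus control on raw differences.** Let a common factor k multiply lipid-day values. An unchanged metabolite with glycerol-day level B then shows an apparent change of B(k − 1). The patient-minus-control difference is (k − 1)(B_patient − B_control), which is zero only if the groups have the same level. Section V specifies differences and mentions no log transform.

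**Step 5: effect on a test.** This uses 8 pairs and a paired t-test on log change at two-sided 0.05 (sidedness assumed). The SD of log change is assumed to be 0.15-0.25 and the within-pair correlation 0-0.5. The chance of a false positive is then 0.07-0.13 at a spurious ratio of 0.95, and 0.19-0.71 at 0.86.

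**Step 6: a stable normaliser.** If neither infusion nor genotype changes the denominator, the apparent ratio of an unchanged metabolite is 1.00.

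**The case against.** The strongest reply is that neither size nor direction is established. The plan does not list which known metabolites enter the sum or how much signal each contributes. If 2% or 5% of the signal doubles, the bias is about 2% or 5%. Infused glycerol can cancel or reverse it (Step 2), and ketones are expected to be lower in long-chain patients, which pulls the sum the other way. This stands, and it rules out a categorical claim.

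A reader might infer that unaffected metabolites such as branched-chain amino acids (BCAAs) will appear to fall, and that the rule manufactures the predicted BCAA result. The documents do not support this. The plan expects a true BCAA fall in controls, so they are not unaffected there. If the sum rises more in patients, patients' BCAAs are pushed down more. That would mask the predicted patient-control contrast rather than create it. Only a comparison within controls could imitate the expected fall.

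A shift common to both groups cancels on a log scale, as does a diagnosis effect on the sum that is equal on both days. This also stands, but the plan expects different acylcarnitine levels by group and specifies raw differences.

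Finally, the reach is limited. Power is based on GIR and PDK4 mRNA; Rd, Ra, ectopic fat by spectroscopy, insulin signalling and explant uptake do not use this normaliser; and FFA has its own colorimetric assay. This narrows the point to the Aim 2 metabolomics without answering it.

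**Conclusion.** The point holds in conditional form. The stated rule divides by a quantity that the plan expects to vary with infusion and diagnosis, with no check, so normalised values of other metabolites may be biased. They appear lower if the sum rises on the lipid day relative to the glycerol day, and higher if the glycerol day's sum rises more.

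The 2-38% range rests wholly on the assumed shares (2-30%) and rises (2- to 3-fold), with no glycerol offset. Bias in the patient-control contrast needs the sum to change differently by group if logs are used. On raw differences it can also arise from a common shift when the groups' levels differ. A reader might go further and doubt the main glucose results, but they do not pass through this step.

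**What to change.** Before the metabolomics batch run planned for year 4:

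1. Prespecify a denominator that leaves out the infused and pathway species (FFAs, glycerol, acylcarnitines, ketones). These remain outcomes and leave only the divisor. Alternatively, analyse log-ratios between metabolites, in which the common divisor cancels.
2. Keep the full-sum version as a sensitivity analysis.
3. Report whether total signal, and the restricted total, differ by infusion and diagnosis. A restricted sum is also an assumption, and this report tests it.
4. Use internal-standard normalisation per plasma volume or tissue weight only where aliquot amounts are recorded. The Metabolomics text lists the standards after extraction and drying; in that order they cannot correct for recovery or sample amount. Muscle is weighed before it is cut into pieces, and no weighing of the divided adipose sample is described.

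Items 1 to 3 need no new assay. The cost is re-processing of existing peak data and possibly somewhat more technical variation than with the full sum.

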The following day, the clamp study will begin at approximately 6:00 AM and end at about 4:00 PM (Day 2; **Figure 11**). Indirect calorimetry to measure energy expenditure and respiratory quotient for estimation of fat oxidation will be performed in the last hour of the clamp. The order of the intralipid vs. glycerol/saline infusion during HEC will be randomly assigned. Subjects will rest overnight and consume a standardized breakfast the following day (Day 3) and be discharged to home. Subjects will return 4 months later and repeat the admission with the alternative clamp procedure. If accurate clamp results are not achieved at Visit 1 or 2, the subject may be asked to return for another study visit to repeat the clamp procedure, DEXA, indirect calorimetry and/or biopsies. During periods of hospital recommendations for decreased in-person contact, study visits will be postponed until study staff are notified of return to normal research visit operations.

¹H and ¹³C MRS Procedure: of the liver and muscle: will be performed as previously described(18, 30) prior to (-100 min) and following both clamp procedures. Each subject will complete 4 MRS measurements of liver and muscle lipid content (**Figure 11**). Image-guided, ¹H localized, MRS following high-resolution T-weighted spin-echo imaging will be performed on a Siemens 3T whole-body system. Radiofrequency surface coils will be used for region-of-interest (ROI) voxel localization and spectroscopy data acquisition. Depending on the schedule for the MRS instruments and to allow for more time for a meal before the testing, the MRS measurements may not be completed until approximately 5:30 PM.

MRI of the abdomen to quantify visceral and subcutaneous fat: Although not a primary outcome, these measures will be acquired using a Siemens 3T system as previously described (18, 30).

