analysis of insulin signaling. *Insulin-stimulated FFA and glucose uptake in WAT explants* from umbilical biopsies will be performed as previously established for non-human primate tissue and as shown in our previous publications and in **Figure 8**.(96-98) *Glucose uptake in skeletal muscle biopsies* will be evaluated in samples treated alone or with 10 nM insulin for 30 min and then exposed to 50 μ M 2-NBD-glucose for an additional 30 min. Samples are then washed, fixed in 4% paraformaldehyde, washed in HBSS with 50 mM CoCl₂, and stored in HBSS with 25 mM CoCl₂ until analyzed by confocal microscopy. 2-NBD-glucose incorporation into individual fibers is quantified using image J. Mean fluorescence per fiber is determined using a randomly positioned circular region of interest of cross-sectional images. *Insulin signaling pathway expression and activation* will be analyzed by preparing total protein lysates in RIPA buffer after homogenization in a motor-driven glass-glass homogenizer for muscle and in X buffer for WAT. Lysates are then subjected to standard Western immunoblotting for phosphorylated (activated) IR, Akt, and (in muscle) PKC- Θ , followed by stripping and probing with pan-IR, Akt, and PKC- Θ antibodies to determine general expression levels and for normalization of phospho-antibody signals as previously described.(24, 25, 63) We acknowledge that insulin receptor substrates (IRS)-1 and 2 are important components of the insulin signaling pathway in fat and muscle and are involved in insulin resistance, but it is our experience that analysis of IRS-1/2 activation requires significant amounts of lysate and immunoprecipitation prior to Western immunoblotting, which we are unlikely to acquire from the biopsies that will be obtained. The proposed analysis of IR, Akt, and PKC- Θ should, however, provide sufficient data to ascertain the status of the insulin-signaling pathway in samples from the different treatment groups.

V.

Statistical Analysis:

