In **Table 6**, we show the differences between groups in mean change that can be detected with 80% power at level 0.05 when the sample size per long-chain disorders is 20. For n=10 subjects, we have adequate power for detecting expected differences for GIR and PDK4 mRNA with modest correlation between repeated observations on the same subject and between matched pairs. For GIR, even with zero correlation, we would have about 97% power at level 0.05 to detect the expected difference in change between groups (31.5 vs 5.7) with n=10. For PDK4 mRNA, we could detect the expected difference in change (-0.62 vs -0.18) with 63% power if zero correlation and with 78% power if the correlation is 0.25 between and within n=10 matched patients.

Table 5: Glucose Infusion Rate (GIR), and PDK4 mRNA/actin in healthy controls and hypothesized mean differences in subjects.				
Outcome	Glycerol Infusion	Interlipid Infusion	H_a : mean Δ In Controls and MCAD	H_a : mean Δ In VLCAD and LCHAD/TFP
GIR ($\mu\text{mol}/\text{kg}/\text{min}$) (n=9)	57.2 ± 9.3	25.7 ± 7.8	31.5	5.7
PDK4 (mRNA/actin) (n=10)	0.18 ± 0.06	0.8 ± 0.38	-0.62	-0.18

Data are mean \pm standard deviation from Roden et al and Tsintzas et al. GIR = glucose infusion rate; PDK4 = pyruvate dehydrogenase kinase 4; H_a : mean Δ = hypothesized mean difference.

Table 6: Change between glycerol infusion and interlipid infusion that can be detected between control and the VLCAD, LCHAD/TFP and CPT2 groups with 80% power at level 0.05 with n=20 subjects long-chain FAO disorders.				
Outcome	Mean Δ (Glycerol – Intralipid) Controls	Correlation between observations on the same subjects	Correlation of Δ between matched controls and patients	Mean Detectable Δ (Glycerol – Intralipid)* LCHAD/TFP subjects
GIR	31.5	.25	.25	17.6
	31.5	.50	.25	20.0
	31.5	.50	.50	22.1
PDK4 mRNA	0.62	.25	.25	0.17
	0.62	.50	.25	0.19
	0.62	.50	.50	0.27

Δ = change; * Note that changes smaller than these can be detected with greater power as smaller changes are further from the changes expected in the control groups.

Timeline: Enrollment and clamp procedures will be completed in years 1, 2, and 3. Biopsy assays and insulin signaling measures will be completed real time with collection of the muscle and adipose samples during years 1-3. In year 4, we will batch analyze stored plasma, muscle, and adipose samples for metabolomics to control for run variation of the metabolomics methods, prepare manuscripts and present the results of the project.

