Studies will be reviewed and approved by the OHSU Institutional Review Board (IRB). All subjects will be admitted to the inpatient unit of the Oregon Clinical and Translational Research Institute (OCTRI). Nursing staff and the investigative team will monitor subjects and care for wound or bleeding complications as a result of catheter placement and biopsy. To prevent radiation exposure to a fetus, a urine pregnancy test will be completed for females of child bearing potential prior to each DEXA Scan. Subjects who are pregnant will be excluded. A stable isotope $^2\text{H}_2$ glucose will be given to subjects. As noted above, the safety of stable isotopes is well documented and does not pose an added risk to the subjects (46). Special care will be taken to explain the use of stable isotopes to the subjects and their families. Plasma glucose will be monitored during the clamp procedure. The MD will discharge subjects at the end of each admission after a physical exam, vital signs are normal and they have no complaints of muscle pain. If they do have muscle pain, we will check a plasma creatine kinase (CK) level prior to discharge.

E. Confidentiality

Upon enrollment, subjects will be assigned a unique identifier that will be used instead of their name, medical record number or other personally identifying information. To ensure confidentiality, all data and specimens collected will be kept in locked laboratory facilities. Urine, blood, muscle and adipose samples will be stored with a unique identifier in locked laboratory facilities at OHSU. Long-term storage of blood muscle and adipose will be stored at -80°C and urine samples will be stored at -20 °C in the laboratory of [name]. The laboratory is a locked facility in the [name] at OHSU, Portland, Oregon. Only the PI and study staff will have access to paper records and the key code which will be stored in locked filing cabinets in restricted access offices at OHSU. Computer files of collected data will be password protected and stored on a restricted drive behind the OHSU firewall. The study coordinator will code urine, blood, muscle and adipose samples with the study ID code to remove any identifiable information on the sample prior to sending the samples to other laboratories for analysis. Subject's names or other identifiable information will not be published or shared with outside research facilities.

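### The plan specifies no masking to diagnostic group or infusion when explant images and Western blots are quantified, which leaves the Aim 2 tissue contrasts open to reading bias

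*Combined protocol and SAP*

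**What the plan says.** Section III (Study Design) randomizes the sequence: "The order of the intralipid vs. glycerol/saline infusion during HEC will be randomly assigned". It does not say that anyone is masked to the infusion.

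Section IV (Laboratory analysis of Tissue Biopsies) describes the readings. For muscle explants, "2-NBD-glucose incorporation into individual fibers is quantified using image J", and "Mean fluorescence per fiber is determined using a randomly positioned circular region of interest of cross-sectional images". For signaling, "Lysates are then subjected to standard Western immunoblotting for phosphorylated (activated) IR, Akt" and, in muscle, PKC-theta; the phospho-signals are then normalized to the pan-antibody signal. Adipose explant uptake is done by methods given in earlier publications.

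For spectroscopy, Section III states: "Each subject will complete 4 MRS measurements of liver and muscle lipid content", taken before and after each clamp.

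On timing, the Timeline in Section V says: "Biopsy assays and insulin signaling measures will be completed real time with collection of the muscle and adipose samples". On coding, Section VI.E gives every subject a unique identifier, stores samples under it, and lets the investigator and study staff hold the key. Before samples go to other laboratories the study coordinator "will code urine, blood, muscle and adipose samples with the study ID code to remove any identifiable information on the sample".

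The Aim 2 anticipated results predict less insulin-receptor and Akt phosphorylation, more PKC-theta phosphorylation and less uptake on intralipid in controls and MCAD patients, with none of these signaling changes and no change in uptake in the long-chain groups. The end of Section III says that these changes between infusions will be compared between the groups.

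**The concern.** Image and blot quantification involves human choices: which fibers and fields to image, how many, which images or lanes to reject, and where to set the background. The expected answer for each group and infusion is written into the protocol, and the plan does not keep that information from the person making these choices.

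The design does not remove such a tendency. It attaches to the infusion and the diagnostic group, not to the period, so neither the random sequence nor the order term in the mixed model absorbs it. Matching does not help either, because the tendency would differ between patient and control. At stake is the mechanistic half of the study: whether tissue insulin action is preserved in the long-chain disorders during a lipid load.

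**Working it through.** No figure in the plan depends on masking, so there is none to reproduce. The check is a reading of the whole document, followed by reasoning on where a bias would land.

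**1. What each provision does and does not cover.**

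| Provision | What it limits | What it leaves open |
|---|---|---|
| Randomly positioned region (Section IV) | Placement of the region on muscle cross-sections | Which fibers and fields, and how many; group and infusion stay visible. The preliminary muscle figure (Figure 8) used 36 fibers, but no number is set for trial samples |
| Pan-antibody normalization (Section IV) | Loading differences between lanes | Knowledge of group and infusion |
| Unique identifier (Section VI.E) | Disclosure of identity | Not said to hide group, infusion or visit; study staff can reach the key; spectroscopy data are not mentioned |
| Random order (Section III) | Confounding of infusion with period | Not masking, although a visit number alone would not reveal the infusion |

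**2. Where a tendency would land.** Let the change be intralipid minus glycerol, and let a reader shift the intralipid reading by d_P in patients and d_C in controls. The patient-control contrast is then shifted by d_P − d_C. A tendency of size β that follows the plan's own predictions gives:
- Explant uptake and receptor/Akt phosphorylation, long-chain groups: d_P = 0 and d_C = −β, so the contrast shifts by 0 − (−β) = +β, in favor of the hypothesis. For PKC-theta the signs reverse and the result still favors the hypothesis.
- The same outcomes, MCAD: d_P = d_C = −β, so the shift is 0.
- Ectopic fat by spectroscopy: the Aim 1 hypotheses predict a rise in patients and controls alike, so d_P = d_C = +β. The contrast shift is 0, but each group's rise is overstated by β.
- Rd and basal Ra: calculated from tracer samples by the Steele equations. GIR: the dextrose infusion rate. No image, blot or spectrum reader is involved.

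**3. Illustration of sensitivity.** Inputs: 8 patients per diagnosis (Section II), separate inference by diagnosis at the 0.05 level (Section V), and a two-sided paired t test with df = 7 (my assumption; the plan does not state sidedness). Let b be the shift in units of the SD of the within-subject change, and ρ the correlation of changes within a matched pair. Both are assumptions.

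The SD of the pair difference is SD_change × √(2(1 − ρ)), so the noncentrality is b√8 / √(2(1 − ρ)). For b = 0.5 it is 0.5 × 2.83 / 1.41 = 1.00 at ρ = 0, and 0.5 × 2.83 / 1.00 = 1.41 at ρ = 0.5. The false-positive rates when there is no true difference are:

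| b | ρ = 0 | ρ = 0.25 | ρ = 0.5 |
|---|---|---|---|
| 0 | 5.0% | 5.0% | 5.0% |
| 0.25 | 7.2% | 7.9% | 9.4% |
| 0.5 | 14.0% | 17.1% | 23.2% |
| 1.0 | 40.8% | 51.2% | 68.1% |

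**4. Can the readings be masked?** Section IV has muscle explants fixed and stored until confocal analysis. Section III (Muscle Biopsy Technique) has muscle pieces frozen at once. Both leave a point at which a code can be applied before quantification.

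**The case against.** The best reply is that silence is not evidence of unmasked reading. Several methods are given only by reference to earlier publications, which may describe masked reading. The random region and the normalization do limit discretion, and the outcomes closest to the main hypothesis are not read by eye. All of this stands, and it sets the limits of the point. A careful reader might still infer more than the documents support:

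- **That readers are known to be unmasked.** The plan specifies no masking; it does not say that readers know the group or infusion.
- **That the insulin-sensitivity result is compromised.** Rd, Ra and GIR do not depend on these readings.
- **That spectroscopy biases the group comparison.** The predicted rise is the same in all groups, so a tendency following it would largely cancel there.
- **That only shipped samples are coded.** Section VI.E stores in-house samples under a unique identifier too.
- **That readings are made on the clamp day with the infusion known.** In the Timeline, real-time assay is set against year-4 batching of metabolomics. It does not fix the day of reading, and stored explants allow later reading.
- **That the bias can be sized from the GIR figures in Table 5.** GIR is unaffected, and the documents give no SD for fluorescence, blots or spectra.

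None of this closes the gap for explant images and blots, because no listed safeguard conceals group or infusion.

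**Conclusion.** The point holds in this limited form. The plan leaves the quantification of explant images and blots without specified masking, while stating in advance the direction expected for each group and infusion. The exposed contrasts are the Aim 2 tissue comparisons of the long-chain groups with their controls. For spectroscopy, the exposure is the claim that lipid rises within subjects. That claim still matters, because the argument is that insulin action is preserved despite lipid accumulation.

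The bias is possible, not shown, and its size cannot be derived from the documents. The false-positive rates above rest entirely on assumed shifts; they show how sensitive 8 pairs are and are not a forecast. No sample size or power figure changes. This is a cheap improvement, not a flaw that undermines the trial.

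**What to change.** Add a short procedure to Section IV:

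- The study coordinator, who already codes samples, relabels stored explants and image sets, blot samples and spectroscopy datasets with random accession numbers that hide group, infusion and visit and, for spectroscopy, time point.
- The number of fibers and fields per sample, and the rule for choosing them, are fixed in advance for muscle and adipose explants.
- Images, blots and spectra are quantified under code. The key is kept from the readers until the values are locked.
- The plan states openly that clamp staff, and staff doing the fresh explant incubation, may remain unmasked.

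The cost is a small labelling burden on existing staff. No extra reader, visit or procedure is needed.
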